7.4.6. General Guidance for Concomitant Therapy

Abemaciclib is predominantly cleared by oxidative metabolism via CYP3A4. Clinical drug interaction studies with a CYP3A inhibitor and CYP3A inducer significantly altered the PK of abemaciclib and its circulating major metabolites.

CYP3A inducers

Avoid concomitant use of CYP3A inducers and consider alternative agents.

CYP3A inhibitors

Avoid concomitant use of strong CYP3A inhibitors (for example, voriconazole) and use caution with coadministered moderate (for example, ciprofloxacin) or weak (for example, ranitidine) CYP3A inhibitors. If coadministration with a strong CYP3A inhibitor is unavoidable, reduce the abemaciclib dose to 100 mg twice daily or, in the case of ketoconazole, reduce the abemaciclib dose to 50 mg twice daily. In patients who have had a dose reduction to 100 mg twice daily due to adverse reactions, further reduce the abemaciclib dose to 50 mg twice daily. Avoid grapefruit or grapefruit juice. If a CYP3A inhibitor is discontinued, increase the abemaciclib dose (after 3-5 half-lives of the inhibitor) to the dose that was used before starting the inhibitor.

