7.3.8 Dose Delays/Modifications

Dose Modifications for Adverse Reactions

The recommended abemaciclib dose modifications for adverse events are provided in table below. Discontinue abemaciclib for participants unable to tolerate 50 mg twice daily. Once the drug is reduced, there is no dose re-escalation.

Abemaciclib Dose Modification for Adverse Reactions

| Dose Level | Abemaciclib Dose |
|---------------------------|--------------------|
| Recommended starting dose | 200 mg twice daily |
| First dose reduction | 150 mg twice daily |
| Second dose reduction | 100 mg twice daily |
| Third dose reduction | 50 mg twice daily |

Guidelines for Dose Adjustments and Delays of Abemaciclib

| Toxicity Type | Toxicity Profile and Severity | Dose Modification | Dose Reduction |
|--------------------------------------------------|----------------------------------|---------------------------------------------------------|------------------------------------------------------------------------------------------------------------------------------------------|
| Hematologic Toxicity | Grade 3 | Dose MUST be held until toxicity resolves to ≤ Grade 2. | Dose MAY be reduced by 1 dose level at investigator's discretion. |
| Hematologic Toxicity (second or more recurrence) | Grade 3 | Dose MUST be held until toxicity resolves to ≤ Grade 2. | Dose MUST be reduced by 1 dose level with each occurrence. Discontinue abemaciclib for participants unable to tolerate 50 mg twice daily |
| Hematologic Toxicity | Grade 4 | Dose MUST be held until toxicity resolves to ≤ Grade 2. | Dose MUST be reduced by 1 dose level. Discontinue abemaciclib for participants unable to tolerate 50 mg twice daily |

| Nonhematologic Toxicity (except diarrhea and ALT increased) | Persistent or recurrent Grade 2 that does not resolve with maximal supportive measures within 7 days to baseline or Grade 1 | Dose MUST be held until toxicity resolves to either baseline or ≤ Grade 1. | Dose MUST be reduced by 1 dose level. Discontinue abemaciclib for participants unable to tolerate 50 mg twice daily |
|----------------------------------------------------------------------|-----------------------------------------------------------------------------------------------------------------------------|----------------------------------------------------------------------------|-----------------------------------------------------------------------------------------------------------------------------|

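### Sections 7.3.8 and 7.4.6 lead to different doses for a participant whose dose was reduced for toxicity during a permitted CYP3A inhibitor course

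*Combined protocol and SAP*

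**What the plan says.** Section 7.3.8 opens with the heading "Dose Modifications for Adverse Reactions". It sets a ladder of 200, 150, 100 and 50 mg twice daily and requires discontinuation if 50 mg is not tolerated. It adds: "Once the drug is reduced, there is no dose re-escalation". Its table makes some reductions mandatory, for example one level down after a Grade 4 hematologic toxicity.

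Section 7.4.6 deals with CYP3A inhibitors in one paragraph, in this order:
- For inhibitors that are not strong, investigators should "use caution with coadministered moderate (for example, ciprofloxacin) or weak (for example, ranitidine) CYP3A inhibitors". No dose change is given.
- If a strong inhibitor cannot be avoided, they should "reduce the abemaciclib dose to 100 mg twice daily or, in the case of ketoconazole, reduce the abemaciclib dose to 50 mg twice daily".
- For earlier toxicity: "In patients who have had a dose reduction to 100 mg twice daily due to adverse reactions, further reduce the abemaciclib dose to 50 mg".
- When the inhibitor stops, they should "increase the abemaciclib dose (after 3-5 half-lives of the inhibitor) to the dose that was used before starting the inhibitor". The sentence speaks of a CYP3A inhibitor without limiting it to strong ones.

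Section 7.3.7 excludes all strong CYP3A inhibitors from the trial and says so twice. It reports predicted exposure increases for two moderate inhibitors but does not exclude them.

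**The concern.** Both sentences can apply to the same participant at the same moment. Suppose someone starts a permitted moderate inhibitor, has a toxicity for which 7.3.8 requires a lower dose, and then finishes the inhibitor. Section 7.3.8 keeps the reduced dose. Section 7.4.6 names a target, the dose before the inhibitor, and so raises a dose that 7.3.8 required to be lowered.

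The 7.4.6 paragraph does consider adverse-reaction reductions, but only one already in place when a strong inhibitor is started. It is silent on a reduction made during the course. What is at stake is participant safety and consistent dosing: two people reading the protocol at the one center could give the same participant different doses, each with support in the text.

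**Working it through.** The plan states no figure to reproduce here. The check traces the protocol's own ladder through both rules. All doses are mg twice daily.

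**Inputs**
- Ladder 200, 150, 100, 50; discontinue if 50 is not tolerated (7.1.6, 7.3.8).
- Moderate or weak inhibitor: no dose change on starting it (7.4.6).
- Strong inhibitor other than ketoconazole: to 100, or to 50 if already at 100 for toxicity (7.4.6).
- Ketoconazole: to 50 (7.4.6).
- One toxicity reduction of one level during the course (7.3.8).

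**Rule.** Let A be the dose before the inhibitor and B the dose after the toxicity reduction. When the inhibitor stops, 7.4.6 gives A and 7.3.8 gives B. The ratio is A/B.

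**Permitted moderate or weak inhibitor**

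| Before (A) | On inhibitor | After toxicity (B) | 7.4.6 gives | 7.3.8 gives | A/B |
|---|---|---|---|---|---|
| 200 | 200 | 150 | 200 | 150 | 200/150 = 1.33 |
| 150 | 150 | 100 | 150 | 100 | 150/100 = 1.5 |
| 100 | 100 | 50 | 100 | 50 | 100/50 = 2 |
| 50 | 50 | discontinue | – | – | no conflict |

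**Strong inhibitor (excluded by 7.3.7, but given a dose rule in 7.4.6)**

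| Case | Before (A) | On inhibitor | After toxicity (B) | 7.4.6 gives | 7.3.8 gives | A/B |
|---|---|---|---|---|---|---|
| Not ketoconazole | 200 | 100 | 50 | 200 | 50 | 200/50 = 4 |
| Not ketoconazole | 150 | 100 | 50 | 150 | 50 | 150/50 = 3 |
| Not ketoconazole | 100 | 50 | discontinue | – | – | no conflict |
| Ketoconazole | 200, 150 or 100 | 50 | discontinue | – | – | no conflict |
| Any strong | 50 | no entry | – | – | – | not covered |

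**Reduction made only because of the inhibitor.** With no toxicity, 7.4.6 restores A. Taken out of context, 7.3.8 would hold the lower dose. Its adverse-reaction heading allows the reading that it does not reach such a reduction, so the two sections can stand together in that case.

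**Frequency.** The 200 mg monotherapy study in Section 2.4.2 reports dose reductions for adverse reactions in 49% and infections in 31%. From those two margins alone, the share of patients with both lies anywhere between 0% (0.49 + 0.31 is below 1) and 31% (the smaller margin). Even that range says nothing about whether the infection was treated with a CYP3A inhibitor or whether the reduction fell within the course. No usable rate follows.

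**The case against.** The strongest reply is that the rules have different scopes. The ban on re-escalation belongs to the adverse-reaction section. The return sentence closes a paragraph about lowering the dose for an inhibitor, so its natural purpose is to undo that lowering. For moderate and weak inhibitors 7.4.6 lowers nothing, so on this view there is nothing to restore.

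This narrows the point but does not remove it. The return sentence is not tied to an interaction-related reduction. It covers a CYP3A inhibitor in general and fixes the target as the earlier dose. The reduction at issue is one for toxicity, which is squarely inside 7.3.8. A reader has to supply the limitation that the text omits.

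Other parts of the reply stand in full:
- A reader might take the fourfold gap as the size of the problem. It requires a strong inhibitor, which 7.3.7 excludes, so it belongs to the separate inconsistency between 7.3.7 and 7.4.6.
- A reader might infer that a participant at 50 mg would be raised to 100 mg when a strong inhibitor is added. The instruction there is to reduce, so the fair description is a missing entry.
- A reader might picture different sites dosing differently. Section 7.1.3 describes a single center; further sites are only a future possibility.

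**Conclusion.** The point holds in limited form. For a toxicity reduction made during a permitted moderate or weak inhibitor course, the literal texts of 7.3.8 and 7.4.6 give doses one ladder step apart, a ratio of 1.33 to 2, and nothing in the protocol says which prevails. This assumes one reduction of one level during the course and a literal reading of the return sentence. A narrower reading of that sentence is possible but is not written down.

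Two stronger conclusions are not supported. One is that the sections contradict each other for every reduction; the heading of 7.3.8 allows them to be reconciled when the inhibitor was the only reason. The other is that the pilot's tolerability result would turn on which sentence is followed. The primary endpoint is response rate (8.4.1), safety is summarized descriptively (8.5.2), and no planned analysis is by dose received. What is affected is the dosing and safety record of any participant who meets this sequence, at a frequency that cannot be derived.

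It is still worth correcting, because it concerns a dose after toxicity in a study of about 10 evaluable participants.

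**What to change.** - Reconcile 7.3.8 and 7.4.6 so that a single dose results when the dose was reduced for an adverse reaction during a CYP3A inhibitor course. State in 7.4.6 whether the return instruction covers such reductions, state in 7.3.8 whether the ban covers reductions made only for an interaction, and cross-refer the two.
- Reconcile the exclusion of strong inhibitors in 7.3.7 with the strong-inhibitor dose rule in 7.4.6. If that rule is kept, say what applies to a participant already at 50 mg twice daily.

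Which rule governs is for the sponsor and medical monitor to decide; no dose or rule is proposed here. The cost is a few sentences in a protocol amendment, with no added visits, tests or participants.

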7.4.7 General Guidance for use of Radiotherapy in Combination with Abemaciclib

Limited data are available on the use of radiotherapy in combination with abemaciclib or alternate dosing schedules (e.g. induction phase). Caution should be exercised with co-administering abemaciclib with radiotherapy.

7.5 Use in Special Populations

7.5.1 Pregnancy

Risk Summary

Based on findings in animals and its mechanism of action, abemaciclib can cause fetal harm when administered to a pregnant woman. There are no available human data informing the drug-associated risk. Advise pregnant women of the potential risk to a fetus. In animal reproduction studies, administration of abemaciclib during organogenesis was teratogenic and caused decreased fetal weight at maternal exposures that were similar to human clinical exposure based on AUC at the maximum recommended human dose.

The background risk of major birth defects and miscarriage for the indicated population is unknown. However, the background risk in the U.S. general population of major birth defects is 2 to 4% and of miscarriage is 15 to 20% of clinically recognized pregnancies.

Data

Animal Data

In an embryo-fetal development study, pregnant rats received oral doses of abemaciclib up to 15 mg/kg/day during the period of organogenesis. Doses ≥4 mg/kg/day caused decreased fetal body weights and increased incidence of cardiovascular and skeletal malformations and variations. These findings included absent innominate artery and aortic arch, malpositioned subclavian artery, unossified sternebra, bipartite ossification of thoracic centrum, and rudimentary or nodulated ribs. At 4 mg/kg/day in rats, the maternal systemic exposures were approximately equal to the human exposure (AUC) at the recommended dose.

7.5.2 Lactation

Risk Summary

There are no data on the presence of abemaciclib in human milk, or its effects on the breastfed child or on milk production. Because of the potential for serious adverse reactions in breastfed infants from abemaciclib, advise lactating women not to breastfeed during abemaciclib treatment and for at least 3 weeks after the last dose.

7.5.3 Females and Males of Reproductive Potential

Pregnancy Testing

Based on animal studies, abemaciclib can cause fetal harm when administered to a pregnant woman Pregnancy testing is recommended for WOCP prior to initiating treatment with abemaciclib.

Contraception

Females

Abemaciclib can cause fetal harm when administered to a pregnant woman [see Use in Specific Populations (8.1)]. Advise females of reproductive potential to use effective contraception during abemaciclib treatment and for at least 3 weeks after the last dose.

Infertility

Males

Based on findings in animals, abemaciclib may impair fertility in males of reproductive potential [see Nonclinical Toxicology].

7.5.4 Pediatric Use

The safety and effectiveness of abemaciclib have not been established in pediatric patients.

7.5.5 Geriatric Use

Of the 900 patients who received abemaciclib in MONARCH 1, MONARCH 2, and MONARCH 3, 38% were 65 years of age or older and 10% were 75 years of age or older. The most common adverse reactions (≥5%) Grade 3 or 4 in patients ≥65 years of age across MONARCH 1, 2, and 3 were neutropenia, diarrhea, fatigue, nausea, dehydration, leukopenia, anemia, infections, and ALT increased. No overall differences in safety or effectiveness of abemaciclib were observed between these patients and younger patients.

7.5.6 Renal Impairment

No dosage adjustment is required for patients with mild or moderate renal impairment (CLcr ≥30-89 mL/min, estimated by Cockcroft-Gault [C-G]). The pharmacokinetics of abemaciclib in patients with severe renal impairment (CLcr <30 mL/min, C-G), end stage renal disease, or in patients on dialysis is unknown.

7.5.7 Hepatic Impairment

No dosage adjustments are necessary in patients with mild or moderate hepatic impairment (Child-Pugh A or B).

Reduce the dose when administering abemaciclib to patients with severe hepatic impairment (Child-Pugh C).

7.6 Procedures for Monitoring Participant Compliance

The Principal Investigator will be responsible for monitoring participant compliance. If the Principal Investigator determines that the participant is not in compliance with the study protocol, the Principal Investigator should determine whether the participant should be withdrawn.

The investigator or designee will instruct the participants on how to take the study drug, demonstrate how to complete the participant's diary card with a record of the number of capsules of abemaciclib that he or she has taken daily at home, and instruct him or her to bring the diary card back for each study visit. The investigator or designee will be responsible for checking the return of study drug and the participant's diary card for completeness at each study visit.

7.7 Assessment of Efficacy

Efficacy of treatment with abemaciclib will be assessed by tumor response. Tumor response assessments for participants with measurable disease will be performed every 8 weeks \pm 7 days for the duration of the treatment period and compared with assessments performed at screening. Tumor response is defined for each participant as the best response during the study as determined using RECIST v 1.1 criteria and tumor specific criteria as described below. Responses will be confirmed with a subsequent radiographic evaluation which would be performed 4 weeks after response is declared. Responses will be recorded as CR, PR, Stable Disease (SD) or Progressive Disease (PD).

7.7.1 Assessment of Tumors by RECIST v 1.1

Tumor assessments that are made after administration of study drug will be compared with those obtained at baseline or the smallest sum since treatment started, to determine whether CR, PR, SD or PD has occurred.

Measurable disease, measurable lesions, and non-measurable lesions are defined as follows:

- Measurable disease: presence of at least 1 measurable lesion after the histological diagnosis and staging of disease
- Measurable lesions: lesions that can be accurately measured in at least 1 dimension as 10 mm or greater and lymph nodes ≥ 15 mm in shortest axis by CT scan measurements (or MRI, as appropriate); prior sites of loco-regional therapy (e.g., fibrosis from radiation) should not be considered measurable lesions
- Non-measurable lesions: all other lesions including skin lesions, small lesions (less than 10 mm), lymph nodes < 15 mm and > 10 mm in shortest axis, ascites, pleural/pericardial effusions, etc.

Documentation of lesions should include date, site, dimensions, description, and diagnostic method. The same method of assessment and technique should be used at baseline and during follow-up to characterize each identified and reported lesion.

Baseline documentation of target and non-target lesions is as follows: all measurable lesions up to a maximum of 5 lesions total and a maximum of 2 lesions per organ representative of all involved organs should be identified as target lesions.

Response Evaluation Criteria in Solid Tumors (RECIST, Version 1.1)

| Measurable tumor burden | Maximum 5 target lesions in total (up to 2 per organ) can be identified at baseline and measured through the course of therapy | |
|----------------------------------|-------------------------------------------------------------------------------------------------------------------------------------------------------------------------------------------------------------------------------------------------------------|--|
| Minimum | ≥10 mm in LD and 2 times the slice thickness for extranodal lesions | |
| size of | ≥15 mm in short axis diameter (SAD) for nodal lesions | |
| measurable | ≥10 mm in LD for clinical lesions (must be measured using electronic calipers) | |
| lesions | ≥20 mm in LD for chest X-ray (if clearly defined and surrounded by aerated lung): CT scan is preferable | |
| | Ultrasound cannot be used to measure lesions | |
| Lymph nodes | Lymph nodes are considered pathologically enlarged if >10 mm in SAD. To be measurable, nodal lesions must be \geq 15 mm in SAD. Nodal lesions with SAD >10 mm and <15 mm are non-measurable. | |
| | The sum of the diameters (LD for extranodal target lesions, SAD for nodal lesions) is followed through the course of therapy. | |
| Bone lesions | A lytic or mixed lytic-blastic bone lesion with a soft tissue component assessed on CT scan/MRI can be measurable if the minimum size criteria are met. Blastic bone lesions and bone lesions assessed on bone scan, PET, or plain film are non-measurable. | |
| Cystic lesions | Lesions that meet the criteria for radiographically defined simple cysts are not malignant. Cystic lesions thought to be metastases can be measurable if they meet the minimum size criteria. Non-cystic lesions are preferable. | |
| Lesions with prior local therapy | Lesions in previously irradiated areas (or areas treated with local therapy) are not measurable unless the lesion has progressed since therapy. Conditions should be defined in study protocols. | |
| Too small to measure | If a target lesion becomes too small to measure, a default value of 5 mm is assigned. If the lesion disappears, the measurement is recorded as 0 mm. | |
| FDG/PET | New lesions can be assessed using FDG-PET: | |
| | (-) PET at baseline and (+) PET at follow-up is PD based on a new lesion. | |
| | No PET at baseline and (+) PET at follow-up is PD if the new lesion is confirmed on CT. If a subsequent CT confirms the new lesion, the date of PD is the date of the initial PET scan, not the CT scan. | |
| (Eigenhauer et el | No PET at baseline and a (+) PET at follow-up corresponding to a pre-existing lesion on CT that is not progressing: not PD | |

(Eisenhauer et al 2009) LD=longest diameter; SAD=short axis diameter; CT=computed tomography; MRI=magnetic resonance imaging; PET=positron emission tomography; FDG=fluorodeoxyglucose

Evaluation of Target Lesions

Target lesions will be evaluated as follows:

| Response | Criteria | |
|----------|----------------------------------------------------------------------------------------------------------------------------|--|
| CR | Disappearance of all target lesions | |
| PR | At least a 30% decrease in the sum of the longest diameter (LD) of target lesions, taking as reference the baseline sum LD | |

| Response | Criteria | | |
|----------|-------------------------------------------------------------------------------------------------------------------------------------------------------------------------------------------|--|--|
| PD | At least a 20% increase in the sum of the LD of target lesions, taking as reference the smallest sum LD recorded since the treatment started or the appearance of one or more new lesions | | |
| SD | Neither sufficient shrinkage to qualify for PR nor sufficient increase to qualify for PD, taking as reference the smallest sum LD since the treatment started | | |

Evaluation of Nontarget Lesions

Nontarget lesions will be evaluated as follows:

| Response | Criteria | | |
|------------------------|----------------------------------------------------------------------------------------------------------------------------------------------------------------------------------------------------------------------------------------------------------------------------------------------------------------------------------------------------------|--|--|
| CR | Disappearance of all non-target lesions and normalization of tumor marker level | | |
| Incomplete response/SD | Persistence of 1 or more non-target lesion(s) and/or maintenance of tumor marker level above the normal limits | | |
| PD | Appearance of 1 or more new lesions and/or unequivocal progression of existing non-target lesions. (Although a clear progression of "non-target" lesions only is exceptional, in such circumstances, the opinion of the treating physician should prevail and the progression status should be confirmed later on by the review panel [or study chair].) | | |

Evaluation of Best Overall Response

The best overall response is the best response recorded from the start of the treatment until disease progression/recurrence (taking as reference for PD the smallest measurements recorded since the treatment started). In general, the participant's best response assessment will depend on the achievement of both measurement and confirmation criteria, as follows:

| Target lesions | Non-target lesions | New lesions | Overall response |
|----------------|------------------------|-------------|------------------|
| CR | CR | No | CR |
| CR | Incomplete response/SD | No | PR |
| PR | Non-PD | No | PR |
| SD | Non-PD | No | SD |
| PD | Any | Yes or no | PD |
| Any | PD | Yes or no | PD |
| Any | Any | Yes | PD |

Participants with a global deterioration of health status requiring discontinuation of treatment without objective evidence of disease progression at that time should be classified as having "symptomatic deterioration." Every effort should be made to document the objective progression, even after discontinuation of treatment. In some circumstances it may be difficult to distinguish residual disease from normal tissue. When the evaluation of CR depends on this determination, it is recommended that the residual lesion be investigated (fine needle aspirate/biopsy) to confirm CR status.

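### Section 7.7.1 follows target lymph nodes by short axis in one table but defines PR, SD and PD on longest diameter in the next

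*Combined protocol and SAP*

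**What the plan says.** Two tables in section 7.7.1 bear on this.

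- **Measurement table, lymph node row.** "The sum of the diameters (LD for extranodal target lesions, SAD for nodal lesions) is followed through the course of therapy". The same table makes a node measurable only at a SAD of 15 mm or more, and calls it pathologically enlarged only above 10 mm SAD.
- **Response table, Evaluation of Target Lesions.** PR is "At least a 30% decrease in the sum of the longest diameter (LD) of target lesions", measured from the LD sum at baseline. PD begins "At least a 20% increase in the sum of the LD of target lesions", measured from the smallest sum on treatment. SD is the remainder, "taking as reference the smallest sum LD since the treatment started". None of these rows mentions SAD. CR requires every target lesion to have gone, with no separate rule for nodes.

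Section 7.7 says that best response is judged "as determined using RECIST v 1.1 criteria and tumor specific criteria as described below". Section 8.4.1 defines the primary endpoint, ORR, by RECIST v1.1 without pointing to either table. No passage says which table prevails.

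**The concern.** A target node qualifies by its short axis, and the measurement table follows it by short axis. The rows that turn the sum into a response category use the long axis. An assessor cannot do both. Two assessors, or one assessor and the statistician checking the derivation, could follow the same section faithfully and record different categories for the same scan.

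The categories feed three endpoints. ORR counts CR and PR, DCR counts CR, PR and SD, and PFS takes its progression date from PD. A PR/SD disagreement changes ORR. An SD/PD disagreement can change DCR and the PFS date. With a target of 10 evaluable patients, a single disputed call is visible in the primary result.

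**Working it through.** The plan gives no figure to reproduce: the sample size of 10 is stated without a formula. The check applies the protocol's own cut-offs to hypothetical lesions.

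**Inputs.** PR at −30% or beyond and PD at +20% or beyond (section 7.7.1, response table); LD outside nodes and SAD for nodes (measurement table); at least 10 evaluable patients and up to about 20 enrolled (section 7.1.3).

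**Formula.** Percentage change = 100 × (new sum − reference sum) / reference sum. The reference is baseline for PR and the smallest sum for PD; in these examples baseline is also the smallest prior sum.

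**A sole nodal target.** Sizes are LD × SAD in mm, and every starting SAD is at least 15 mm.

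| Change in node | By LD | Call | By SAD | Call |
|---|---|---|---|---|
| 24×16 to 20×11 | 20/24 − 1 = −16.7% | SD | 11/16 − 1 = −31.3% | PR |
| 22×18 to 15×14 | 15/22 − 1 = −31.8% | PR | 14/18 − 1 = −22.2% | SD |
| 30×20 to 36×22 | 36/30 − 1 = +20.0% | PD | 22/20 − 1 = +10.0% | SD |
| 28×16 to 30×20 | 30/28 − 1 = +7.1% | SD | 20/16 − 1 = +25.0% | PD |

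The calls disagree in both directions, for response and for progression. If both axes change by the same percentage, they agree.

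**A node with a liver lesion.** The liver lesion goes from 40 to 30 mm and the node from 30×20 to 24×12 mm.

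- LD for both: (40 + 30) to (30 + 24), so 54/70 − 1 = −22.9%, SD.
- LD for liver, SAD for node: (40 + 20) to (30 + 12), so 42/60 − 1 = −30.0%, PR.

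**Weight of one changed call.** 1/10 = 10 points of ORR; 1/20 = 5 points. At n = 10, going from 0 to 1 responder moves the exact 95% interval from 0–30.8% to 0.3–44.5%.

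**The CR row.** A target node starts at 15 mm SAD or more. If it falls to 10 mm or less it is no longer enlarged by the protocol's definition, and its SAD is down by at least (15 − 10)/15 = 33.3%. If the extranodal targets have gone as well, the SAD-based sum is also down by at least 33.3%. The target lesions therefore already meet PR. Once SAD is used, the CR wording alters only the split between CR and PR. Under the LD rows this is not assured: a node going from 22×15 to 16×10 mm is 16/22 − 1 = −27.3%, SD.

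**The case against.** The best defence is that LD in the response table is shorthand. The measurement table is headed RECIST v1.1 and states which diameter enters the sum, and sections 8.0 and 8.4.1 name RECIST v1.1. In section 7.7 the closing words about criteria described below may attach only to the tumor-specific criteria, so it is too strong to say that the response table must govern. This part of the objection stands: the short-axis reading is probably what was meant. It does not remove the contradiction. The response rows spell out longest diameter and make no exception, both tables sit under the same heading, and the RECIST publication cited beneath the measurement table is missing from the References.

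Three stronger readings are tempting, and the documents do not support them.

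- **That the lack of a millimetre minimum for PD is a second contradiction.** Neither table gives such a minimum, so nothing is contradicted, and the RECIST publication is not part of the documents. The effect is also narrow. The protocol says "If a target lesion becomes too small to measure, a default value of 5 mm is assigned", so a sole target read as 5 and then 6 mm is +20%; but a 1 mm rise suffices only at a smallest sum of 5 mm or less. At 10 mm it takes 2 mm, and at 25 mm it takes 5 mm.
- **That a normalised node can never be CR.** Section 7.7.1 advises aspirate or biopsy where residual disease is hard to tell from normal tissue and CR depends on it. After the main correction the CR row does not affect ORR or DCR.
- **That the LD rows bias ORR downward.** The second node in the working table is a PR by LD and SD by SAD, so the error can run either way.

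**Conclusion.** The contradiction between the measurement table and the PR, PD and SD rows is real and touches the rule that defines the primary endpoint. It can misclassify a patient; it does not do so routinely. It needs a target node whose axes change by different percentages, near enough to a cut-off for the category to change.

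The size is 10 points of ORR per changed call if 10 patients are analysed and 5 points if 20 are. The documents do not say how many patients will have nodal target lesions, so neither the expected number of changed calls nor their net direction can be estimated. The lesion sizes in the working are illustrations and not data from this trial.

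The CR row is a minor consistency matter. The absence of a millimetre minimum for PD is not part of this finding.

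**What to change.** In the PR, PD and SD rows, and in the reference sums they name, replace the sum of longest diameters with the sum the measurement table already defines: LD for target lesions outside nodes, SAD for nodal ones.

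Separately, reconcile the CR row with the protocol's own threshold of more than 10 mm SAD for an enlarged node, so that the status of a target node at or below that size is stated.

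The cost is table wording. A node must already be measured by SAD to qualify as a target, and section 7.7.1 already asks for lesion dimensions to be documented, so no new scans, visits or measurements follow. If any patients have already been assessed, the nodal calls should be checked against the corrected rows and any change of category reported. No percentage cut-off changes, and no millimetre threshold is proposed.
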